## ASSESSMENT TOOLS AND DATA COLLECTION

### *Profiling/Characteristics of the Sample*

Demographic characteristics (age, gender, education level, marital/living status, employment status) will be determined from the patient's self-report. Clinical characteristics (diagnosis, illness duration, medications and other treatments) will be determined from the patient's self-report, review of medical record, and Karnofsky Performance Status.

### *Outcome Assessment*

Outcome assessment will utilize the following tools:

- Patients's Daily Diaries will be used to take notes of days on which a migraine attack occurs, duration of the attack, severity of migraine pain during the migraine attack, acute antimigraine drug use, and occurrence of any other (non-migraine) headache. Time needed to fill-in the diary is about 1-3 minutes per day (filled-in only on days when headache or migraine medication intake occur).
- Pain Numerical Rating Scale (Pain NRS) is an eleven point [0-10] scale for rating of pain intensity, with the anchor points 0=no pain and 10=worst pain imaginable. Administration time is about 1 minute, rated only on migraine days.

- Migraine-Specific Quality of Life Questionnaire (MSQ) is a validated 25-item questionnaire evaluating impact of migraine on physical, emotional and social component of patients' life. Recall period is four weeks. Administered at the baseline, at the end of month 1 and month 2 of tDCS/sham application. Administration time is about 5 minutes (Rendas-Baum et al., 2013).
- Hamilton Depression Scale (HamD) is a validated 17-item instrument for assessment of depressive symptoms. Administered at the baseline, at the end of month 1 and month 2 of tDCS/sham application. Administration time is about 20 minutes (Hamilton, 1960; Williams, 1988).
- tDCS User Survey is an 8-item questionnaire on user's satisfaction with the use of tDCS. Administered at the end of tDCS use. Administration time is about 5 minutes.
- Occurrence of side effects and adverse events through the study. Tolerability will be determined from occurrence of side effects and adverse events related, probably related or possibly related to tDCS, through the study.

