The study will include 60 adults from general population of the New York metropolitan area, of age 18-65 years, who experience 4 migraine days or more per month and fully meet the Inclusion/Exclusion criteria described in detail below in the study protocol. For each participant the study will last about 90 days (30 days of the baseline followed by 60 days of the study intervention), and involve 3 study visits. At Visit 1, patients will provide written informed consent and undergo screening for the eligibility. This will be followed by 30 days of baseline at home during which patients will keep daily records of migraine occurrence and provide answers to a set of symptom-related questionnaires. Patients with 4 or more migraine days per month who fully meet the study eligibility criteria at the end of the baseline period will be randomized in double-blind manner into two groups: Group 1 will be randomized to receive active tDCS in daily 20-minute applications for 60 days; Group 2 will be randomized to receive sham tDCS in daily 20-minute applications for 60 days, self-applied at home. Following randomization, Visit #2 will be held either in the patient's home or in the research facility, based on the patient's preference. tDCS device will be deployed to the patient and instructions on tDCS use will be provided. The first tDCS/sham self-application by the patient will be done at Visit 2. Daily tDCS/sham self-application by the patient at home will continue for the rest of the 60-day period. Study staff will be in regular remote contact with the patient via phone and HIPAA-compliant videoconferencing. Upon conclusion of the intervention, tDCS device will be collected from the patient at Visit 3 held either in the patient's home or in the research facility, based on the patient's preference. Safety monitoring will continue bi-weekly by phone for 30 days after the last tDCS/sham application. Outcome assessment will be carried out at the end of the baseline, and at the end of month 1 (day 30; secondary end-point) and month 2 (day 60, primary end-point) of the tDCS/sham intervention.

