## **DESIGN AND OVERVIEW**

This study will employ a single-center double-blind randomized sham-controlled two-parallel-arm design and involve 60 adults with migraine. For each participant, the study will involve 3 study visits and last about 90 days (30 days of the baseline followed by 60 days of the tDCS/sham study intervention). A post-study safety monitoring will continue bi-weekly by phone for 30 days after the last tDCS/sham application.

At Visit 1, patients will provide written informed consent and undergo screening for the eligibility. This will be followed by 30 days of baseline at home during which patients will keep daily records (Daily Diaries) of migraine occurrence and provide answers to a set of symptom-related questionnaires. Patients with 4 or more migraine days per month who fully meet the study eligibility criteria at the end of the baseline period will be randomized in double-blind manner into two groups: Group 1 will be randomized to receive active tDCS in daily 20-minute applications for 60 days; Group 2 will be randomized to receive sham tDCS in daily 20-minute applications for 60 days, self-applied at home. Following randomization, patients will continue keeping the Daily Diaries and Visit #2 will be held either in the patient's home or in the research facility, based on the patient's preference. tDCS device will be deployed to the patient and instructions on tDCS use will be provided. The first tDCS/sham self-application by the patient will be done at Visit 2. Daily tDCS/sham self-application by the patient at home and records in the form of Daily Diaries will continue for the rest of the 60-day period. Study staff will be in regular remote contact with the patient via phone and HIPAA-compliant videoconferencing. Upon conclusion of the intervention, Visit 3 held either in the patient's home or in the research facility, based on the patient's preference. tDCS device will be collected from the patient. Safety monitoring will continue bi-weekly by phone for 30 days after the last tDCS/sham application.

Outcome assessment will be carried out at the end of the baseline, and at the end of month 1 (day  $30\pm 2$ ; the secondary end-point) and month 2 (day  $60\pm 2$ , the primary end-point) of the tDCS/sham intervention.

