## **OUTCOME MEASURES AND ENDPOINTS**

Outcome assessment time-points will be at the end of the 30-day baseline ( $\pm 2$  days), at the end of month 1 (day  $30 \pm 2$  days, the secondary end-point) and month 2 (day  $60 \pm 2$  days, the primary end-point) of the tDCS/sham intervention.

The primary comparison will be the between-group comparison at the end of month 2 of the tDCS/sham intervention.

**The primary outcome measure** will be *Change in mean number of migraine days per month.*

A note: A migraine day is defined as any calendar day on which the patient had onset, continuation, or recurrence of a migraine as recorded in the diary. A migraine is defined as a migraine (with or without aura) lasting at least 30 minutes. Any calendar day on which acute migraine medication is used is counted as a migraine day.

**Secondary outcome measures** will be:

1. *Percentage of responders*, determined as a number of patients having at least 50% reduction of monthly migraine days between the one-month baseline and post-intervention, in each of the two study groups;
2. *Change in monthly migraine attack frequency*,
3. *Change in monthly acute antimigraine drug use*,

all determined from the patients' diaries;

4. *Change in mean headache severity per migraine day* determined from Pain NRS ratings on migraine days;
5. *Change in quality of life* determined from ratings on the migraine-specific MSQ questionnaire;
6. *Change in depressive symptoms* determined from the Hamilton Depression Scale (HamD);
7. *Tolerability* determined from occurrence of side effects and adverse events related, probably related or possibly related to tDCS, through the study;
8. *Satisfaction* - percentage of patients stating at the end of the trial that they are very satisfied, moderately satisfied, or not satisfied with the treatment, determined from the 8-item tDCS User Survey at the end of the intervention;

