**Visit #1:** The visit will take place at a designated room at the New York Headache Center. At the visit, the study staff will guide the patient through the process of review and signing the Informed Consent and HIPAA authorization to allow study staff to obtain necessary medical information from patient's medical record. The patient will receive a copy of the signed Informed Consent and HIPAA authorization. Study staff will then collect profiling demographic and clinical characteristics and review medical information for the purpose of eligibility screening. Patients who meet the study Inclusion/Exclusion criteria at screening will receive instructions on how to keep Participant's Daily Diaries and will proceed to the baseline.

**30-day Baseline (at home):** Through the baseline, patients will keep daily diaries to document migraine occurrence, related symptoms and medication intake. The diaries will be sent once a week via encrypted HIPAA-compliant email or by fax to the study personnel. Patients who report 4 or more migraine days per month at the end of the baseline period and fully meet the Inclusion/Exclusion criteria will be eligible to undergo randomization and proceed to the interventional phase of the study.

**Randomization.** Randomization list will be computer generated by study statistician using the block-of-six method. Both the patient and study personnel, except for statistician will be blinded to the sham vs active tDCS treatment assignment. tDCS devices will be programmed to sham or active tDCS mode in accordance with the randomization list.

**tDCS stimulation protocol and device.** The active tDCS will involve 20-minutes of direct current at intensity of 1.5 mA. Sham will include 30 seconds of stimulation at 1.5 mA, followed by 0 mA for the remaining time. The stimulation pads (electrodes) will be placed in a simple headband, as depicted in detail in the Patient tDCS Instructional Brochure. The tDCS device for this study will be *Soterix mini-CT* (Soterix Medical Inc., New York, NY). The tDCS mini-CT was developed for at home administration and has enhanced safety features: a unique keypad access system that allows the user to apply only the pre-determined dose each day. The device will be deployed to the patient at Visit #2.

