**Visit #2 - Familiarization with tDCS and Device Deployment** will be held either at the patient's home or at a designated room at the MJHS Institute, whichever is more convenient for the patient. Familiarization will build on tDCS information provided to the patient via flyer and tDCS booklet prior consenting. The study personnel will demonstrate the equipment and function of the device, instruct the patient on the use of the device, and will review the IRB-approved instructional booklet with the patient. The patient will have an opportunity to experience the sensory sensation associated with tDCS procedure by applying 30 seconds of tDCS stimulation on the arm at the intensity 1.5 mA that is planned be used in the study. The study personnel will also instruct the patient how to establish video connection for a remote contact with the tDCS supervising study personnel located at the MJHS Institute via a HIPAA-compliant Zoom application via the patient's phone, tablet or personal computer. (Patients who do not possess any of these electronic devices will be given an electronic Tablet equipped with Zoom capability for the study duration). At the end of Visit 2, the patient will carry-out the first tDCS/sham application under in-person supervision of study personnel.

**tDCS/Sham Applications in Home Settings.** After the first 20-minute tDCS/sham self-applied by the patient at Visit #2, the tDCS/sham self-applications will continue daily for the total of 60 days. Reminders will be sent by the study personnel via email and text message daily. In addition, study staff will be in regular remote contact with the patient via phone and/or HIPAA-compliant videoconferencing, at least three times per week during the first week and at least twice a week during the remaining weeks.

During the intervention period of the study, patients will continue keeping daily diaries, to document migraine occurrence, related symptoms and medication intake, as done at the baseline period. Patients will receive reminders about the diaries via email and text messages. The diaries will be in electronic form and patients will be sent the diaries to the study site once a week via encrypted HIPAA-compliant email or by fax.

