## Analysis Plan (Update 1.29.20)

Participants will be randomized within randomly selected blocks of sizes 2, 4, and 6. The randomization list will be generated by an investigator not otherwise associated with the administration of treatment or collection of data.

All patient characteristics and outcomes will be evaluated for distribution. For all bivariate tests, the appropriate parametric or non-parametric test will be selected based on distribution. Patient characteristics will be described and bivariate tests will evaluate any differences across treatment group (active tDCS vs. sham tDCS). Primary and secondary outcomes at baseline will be described and bivariate tests will evaluate any differences across group. Bivariate tests will evaluate differences in attrition, patient satisfaction, adverse events (including all adverse events, serious adverse events, and adverse events attributed to the treatment), and quality of blinding across group.

All outcomes will be described using data visualization. Differences in outcome between the active tDCS and sham tDCS groups will be evaluated in both intent-to-treat and completer analysis using non-parametric statistics as appropriate (see Table below). Intent-to-treat analysis will impute missing values using all available data. Differences in outcome between people with chronic (15 or more headache days/month) vs. episodic migraine, with and without medication overuse (e.g., using a MSM on 10 or more days per month during the baseline period), and with high and low levels of patient compliance will also be evaluated using the appropriate non-parametric statistic.

Alpha will be set at 0.05, two-tailed, for all analyses. SPSS v. 25.0 and R will be used for all analyses.

Primary Outcome	Description	Tentative Analysis Type
Change in migraine day/30 day	Median change in the number of migraine days per 30 day period, from M0 to M2.	Mann-Whitney U
Secondary Outcomes		
Responders	% of participants who report a 50% reduction in migraine days, from M0 to M2.	Fisher's Exact Test
Change in headache attack/30 days	Median change in number of attacks per 30 day period, from M0 to M2.	Mann-Whitney U
Change in acute medication use	Median change in number of days on which an acute medication was used from M0 to M2.	Mann-Whitney U
Change in headache attack intensity	Median change in NRS from headache days in a 30 day period from M0 to M2.	Mann-Whitney U

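### The diary is completed only on headache or medication days, so a blank day cannot be told apart from a forgotten one, and the primary outcome counts it as migraine-free

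*Protocol*

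**What the plan says.** The protocol describes the diary in two ways.

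- **Daily.** In the Summary, during baseline "patients will keep daily records of migraine occurrence". Design and Overview says "patients will keep daily records (Daily Diaries) of migraine occurrence" and has the Daily Diaries continue through the 60-day intervention. The baseline paragraph of Study Procedures says "patients will keep daily diaries to document migraine occurrence, related symptoms and medication intake".
- **Event-only.** Outcome Assessment, when giving the time needed, says the diary is "filled-in only on days when headache or migraine medication intake occur".

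Outcome Measures and Endpoints defines a migraine day as "any calendar day on which the patient had onset, continuation, or recurrence of a migraine as recorded in the diary", and also counts any day with acute migraine medication. The SAP measures the change in these days per 30 days from M0 (baseline) to M2 (month 2). On missing data it says: "Intent-to-treat analysis will impute missing values using all available data". Neither document defines a missing diary day.

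Several safeguards bear on diary keeping. Diaries are returned weekly in both periods. During the intervention, staff contact patients at least twice a week and "Patients will receive reminders about the diaries via email and text messages". Diaries are evaluated on day 30 and at Visit 3, and payment depends on completed diaries.

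**The concern.** If only event days are entered, a blank line in a returned diary has two possible meanings: no headache, or a headache that was not written down. The endpoint definition resolves every blank as no migraine. Imputation can handle an unreturned week or a dropout, because those are visibly missing. It cannot handle one forgotten day in a returned week.

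The primary outcome, responder rate, attack frequency, acute drug use and the four-day entry threshold all rest on this instrument. Entered days can be counted and checked for completeness, but the rest cannot be classified. The trial therefore could not show that recording was equal between arms, or between M0 and M2.

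Diary reminders are described only for the intervention, so the conditions of recording differ, as written, between the two periods that the primary outcome subtracts.

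**Working it through.** **1. What a blank day becomes**

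| True state of the day | Diary under the event-only rule | Counted as | Open to imputation? |
|---|---|---|---|
| Well | blank | no migraine | not needed |
| Migraine, entered | entry | migraine day | not needed |
| Migraine, forgotten, week returned | blank | no migraine | no, not identifiable |
| Any, week not returned | no diary | missing | yes |

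The first and third rows look the same. Weekly return, contact, reminders, diary evaluation and payment may make the third row rarer, but none is stated to separate it from the first.

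**2. Shift within an arm**

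Let b be the true migraine days in both months, and q0 and q2 the share of migraine days unrecorded at M0 and M2. The apparent change is −b(q2 − q0). With b = 8:
- q0 = 0.10, q2 = 0.20: −8 × 0.10 = −0.8 day.
- q0 = 0.20, q2 = 0.10: +0.8 day.

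**3. Responder threshold**

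A true reduction r is scored as 50% when (1 − r)(1 − q2)/(1 − q0) = 0.5. With q0 = 0:
- q2 = 0.10: r = 1 − 0.5/0.9 = 44%.
- q2 = 0.20: r = 1 − 0.5/0.8 = 37.5%.

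In the reverse direction (q0 = 0.20, q2 = 0.10), r = 1 − 0.5 × 0.8/0.9 = 56%.

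**4. Between-arm test (simulation)**

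The sample (60 randomized, so 30 per arm), the entry rule and the two-sided 5% Mann-Whitney test come from the documents. The rest is assumed:
- patient rates are gamma with mean 8 days per 30 and shape 4;
- between-month variation is lognormal with log-SD 0.3 and median one, in M2 only (variant A) or in both months (variant B);
- day counts are binomial, and entry requires at least 4 recorded days at M0;
- 10,000 runs per setting.

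Equal lapses in both arms:

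| q0 / q2 | Rejection, no effect (A / B) | Power, true 30% reduction (A / B) |
|---|---|---|
| 0 / 0 | 5.2 / 4.8% | 67.8 / 53.7% |
| 5 / 10% | 5.3 / 4.9% | 64.3 / 50.2% |
| 10 / 10% | 5.4 / 4.7% | 65.1 / 52.0% |
| 10 / 20% | 5.2 / 4.8% | 59.2 / 45.8% |
| 20 / 10% | 5.1 / 4.7% | 67.4 / 56.1% |

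At 10/20% the loss is 67.8 − 59.2 = 8.6 points in A and 53.7 − 45.8 = 7.9 in B. Using mean-one instead of median-one monthly variation lowers the no-lapse power in A to about 65%, but the loss at 10/20% stays of similar size.

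Unequal lapses at M2, no true effect, M0 lapses 10% in both arms:

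| M2 lapses, active vs sham | Spurious difference (days, A) | Rejection (A / B) |
|---|---|---|
| 12.5 vs 10% | −0.23 | 5.5 / 5.2% |
| 15 vs 10% | −0.46 | 6.5 / 6.2% |
| 10 vs 15% | +0.47 | 7.1 / 6.2% |
| 20 vs 10% | −0.93 | 12.9 / 10.5% |
| 10 vs 20% | +0.94 | 13.3 / 10.4% |

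**5. Entry threshold**

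The chance that a patient with t true migraine days records fewer than 4 is P(Binomial(t, 1 − q) ≤ 3).
- q = 0.10: t = 4 gives 1 − 0.9⁴ = 34%; t = 5, 8%; t = 6, 1.6%; t = 8, under 0.1%.
- q = 0.05: t = 4 gives 19%; t = 5, 2%.

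**The case against.** **The wording is a tension, not a flat contradiction.** A daily diary could mean a form with one dated line per day, filled in when something happens. That is fair, but on that reading the blank day remains unclassifiable. The form itself is not in the documents and may have a daily yes/no item. If so, the event-only sentence is wrong as written, and the SAP still needs to define a missing day.

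**The primary comparison is not shown to be biased.** This stands. The protocol says "Both the patient and study personnel, except for statistician will be blinded to the sham vs active tDCS treatment assignment", and contact and reminders are the same in both arms, so equal lapses are the natural expectation. Equal lapses do not inflate the false-positive rate. The unequal-lapse figures show sensitivity, not a predicted error.

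**The power loss needs more lapses in month 2 than at baseline.** The only documented asymmetry, diary reminders and staff contact described for the intervention alone, points the other way. In that direction (20/10%) there is no material power loss, and the within-arm shift goes against treatment. This also stands, and the 8 to 9 points should not be read as the likely cost. The within-group comparisons that a shift would move are labelled secondary and exploratory.

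**Proration can overcorrect.** If patients skip mainly well days, 8 recorded migraine days with 6 well days skipped become 8 × 30/24 = 10, an error of +2 days. This is a good reason to offer proration as one option with a sensitivity analysis. It does not count against daily entry or against coding an unentered day as missing.

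**Conclusion.** The point holds and should be fixed. As written, the event-only rule and the endpoint definition together turn a forgotten migraine day into a migraine-free day, and nothing in the protocol or SAP detects it. The main harm is to verifiability: equal recording between arms and between periods could not be demonstrated.

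No false positive between arms is predicted, provided lapses are equal. The possible power cost runs from nothing material to 8 to 9 points, depending on whether lapses rise from M0 to M2. A within-arm shift would be about 0.8 day for 8 true days and a 10-point change in lapses, in either direction. Lapses during baseline would exclude some patients near four days, which affects recruitment rather than the comparison. All sizes rest on assumed lapse rates and an assumed model. Confidence is moderate because the diary form has not been seen.

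**What to change.** **Protocol.** Bring the Outcome Assessment sentence into line with the Summary, Design and Procedures sections by requiring one short entry every calendar day in baseline and intervention: headache yes/no, acute medication yes/no. Send the same diary reminders during the baseline. If the form already has such an item, correct the sentence.

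**SAP.** State that a day without an entry is missing, not migraine-free, and report entered days by arm and by period. One reasonable way to handle missing days is a minimum number of entered days per 30-day window, proration to 30 days above that minimum, and a sensitivity analysis counting unentered days as migraine-free.

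**Cost.** A few seconds per headache-free day, baseline reminders, one amended diary instruction submitted to the IRB, and one SAP rule. The number randomized is unchanged. Some days or windows that would have counted as zero will be marked missing, so there may be fewer fully observed primary outcomes and more imputation. The diary change must be in place while patients are recording, because an ambiguous blank cannot be reliably resolved afterwards.
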